7.8 SAFETY ANALYSIS

All safety analyses will be performed on the TS, besides the analyses of MTD determination. These will be performed on the MTD evaluation set.

7.8.1 Adverse events

The analyses of AEs will be descriptive in nature. All analyses will be based on the number of patients with AEs (not on the number of AEs). The analysis will be based on BI standards (6). AEs will be coded using the most recent version of MedDRA. According to the BI standards multiple overlapping or adjacent recordings (AE occurrences) of the same AE are collapsed into one AE event if all AE attributes are identical (lower level term, severity, action taken, therapy required, seriousness, reason for seriousness, relationship, outcome, AE of special interest (AESI) flag).

The analyses of AEs will be based on the concept of treatment-emergent AEs, where a treatment-emergent AE has an onset in the analysing treatment period. The AE analysis will be based on the on-treatment period which starts with the date of the first administration of study medication and ends 30 days after the last administration of study medication. AEs with an onset date in the screening period (time between informed consent date and date of the first administration of study medication) or follow-up period (time after the on-treatment period) will be tabulated and listed separately.

Sorting order: In AE tables, system organ classes (SOCs) will be sorted alphabetically and preferred terms (PTs, within SOCs) will be sorted by descending frequency.

Listings of AEs will be displayed by patient. The actual planned dose of BI 891065/dose combination of BI 891065 and BI 754091 will be derived and included in the listings. AEs will be reported with start day and end day as calculated from the first day of treatment with study medication. For listings displaying AEs during the screening or follow-up period, the start and stop day are calculated from the start of the respective analysis period.

The incidence of AEs overall, related AEs, serious AEs (SAEs), and immune-related AEs will be reported by severity according to common terminology criteria for adverse events (CTCAE) grades (CTCAE version 4.03 for Part A, CTCAE version 5.0 for Part B and Part C). Drug-related serious AEs will also be tabulated. Protocol-specified AESI will be analysed based on data reported in the eCRF.

AEs leading to death during the on-treatment period will be tabulated by SOC and PT. Reported fatal AEs during the follow-up period will be listed.

Other significant AEs are defined as serious and non-serious AEs that lead to dose reduction of BI 891065 (for all trial parts) or permanent discontinuation of study medication (BI 891065 in Part A, BI 891065 and BI 754091 in Parts B and C). Their incidence will be reported by severity according to CTCAE grades. A listing of patients who developed other significant AEs will be provided and a flag for serious and non-serious will be included. In addition, AEs leading to treatment interruption will be reported by severity according to CTCAE grades.

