5.2.6.7 Adverse event collection and reporting

5.2.6.7.1 Adverse event collection

The adverse event reporting scheme is presented in [Figure 5.2.6.7.1: 1](#). The Investigator shall maintain and keep detailed records of all AEs in the patient files. The following must be collected and documented on the appropriate eCRF by the Investigator:

- From signing the informed consent onward until the end of treatment including residual effect period (REP):
 - all AEs (non-serious and serious) and all AESIs.
- After the end of treatment including REP until the individual patient's end of trial:
 - all related SAEs and all related AESIs.
- After the individual patient's end of the trial:
 - the Investigator does not need to actively monitor the patient for new AEs but should only report related SAEs and related AESIs of which the Investigator may become aware of by any means of communication (e.g., phone call). Those AEs should however, not be reported in the CRF.

The rules for Adverse Event Reporting exemptions still apply.

[figure not shown]

Figure 5.2.6.7.1: 1 Adverse event reporting scheme

The REP is defined as 30 days after the last trial medication application. All AEs which occurred through the treatment phase and throughout the REP will be considered as on treatment. Events which occurred after the REP will be considered as post treatment events.

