7.3.4 Safety analyses

Adverse events will be coded using the Medical Dictionary for Drug Regulatory Activities (MedDRA). Standard BI summary tables and listings will be produced. All adverse events

with an onset between start of treatment and end of the residual effect period (REP), a period of 30 days after the last dose of trial medication, will be assigned to the on-treatment period for evaluation.

All treated patients will be included in the safety analysis. In general, safety analyses will be descriptive in nature and will be based on BI standards. No hypothesis testing is planned.

Statistical analysis and reporting of adverse events will concentrate on treatment-emergent adverse events, i.e. all adverse events occurring between start of treatment and end of the residual effect period. Adverse events that start before first drug intake and deteriorate under treatment will also be considered as 'treatment-emergent'.

Frequency, severity, and causal relationship of adverse events will be tabulated by system organ class and preferred term after coding according to the current version of the MedDRA at the database lock.

Laboratory data will be analysed both quantitatively as well as qualitatively. The latter will be done via comparison of laboratory data to their reference ranges. Values outside the reference range as well as values defined as clinically relevant will be summarised. Treatment groups will be compared descriptively with regard to distribution parameters as well as with regard to frequency and percentage of patients with abnormal values or clinically relevant abnormal values.

Vital signs, physical examinations, or other safety-relevant data observed at screening, baseline, during the course of the trial and at the end-of-trial evaluation will be assessed with regard to possible changes compared to findings before start of treatment.

Analyses of the centrally evaluated ECG data will be specified in the TSAP.

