4. CHANGES IN THE PLANNED ANALYSIS OF THE STUDY

All analyses described in the CTP will be carried out.

Since t_{max} of BI 891065 appears to be earlier than expected, all ECG recordings collected at the scheduled time points listed in Tables 10:3:1, 10:3:2 and 10:3:3 of the CTP will be analysed.

Part C of this trial is cancelled and enrolled no patients. Hence, no planned analyses for this trial part will be conducted.

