6. GENERAL ANALYSIS DEFINITIONS

6.1 TREATMENT(S)

In this Phase I trial, treatments are not randomized. In Parts A and B, different dose levels of BI 891065 alone (Part A) or of BI 891065 in combination with BI 754091 (Part B) are being administered. In the expansion part (Part C), patients will be treated with the dose combination that has been determined in Part B.

The data will be presented separately for each part, if not specified otherwise. All planned analyses will be presented by initial treatment group, i.e. in Parts A and B for all dose cohorts separately and in total over all dose cohorts of that trial part. Patients where treatment group assignment in terms of dose cohorts within a trial part has not been followed will be handled on a case-by-case basis and will be agreed upon latest at the report planning meeting before database lock of the specific trial part.

For safety summaries events that start from the first administration of any trial medication until 30 days (REP) after the last administration of any trial medication will be considered as having occurred “on-treatment”. If not specified otherwise, all safety tables will be based on the on-treatment period. Adverse events that have onset during the screening or the follow-up period will be displayed in separate listings from those that occurred during the on-treatment period. The MTD evaluation period will be defined as start of cycle 1 + 21 days for all patients. Labels of each analysing treatment period, analysis numbers, the labels used for displays in the tables and listings in the CTR, as well codes, decodes, sort order and labels for each trial medication are provided in the TSAP technical documents.

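### SAP 7.8.1 defines treatment-emergent AEs by onset alone and drops, undeclared, the protocol 7.3.4 rule that pre-dose AEs worsening on treatment also count

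*SAP*

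**What the plan says.** Protocol 7.3.4 (Safety analyses) has three relevant sentences. One assigns to the on-treatment period AEs "with an onset between start of treatment and end of the residual effect period", which is 30 days after the last dose. One takes AEs in that window as treatment-emergent. The third widens the definition: "Adverse events that start before first drug intake and deteriorate under treatment will also be considered as" treatment-emergent.

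SAP 7.8.1 (Adverse events) uses the same window but defines membership by onset only: "a treatment-emergent AE has an onset in the analysing treatment period". AEs whose onset falls between consent and first dose are tabulated and listed separately, with no exception for worsening.

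SAP 6.1 (Treatments) treats as on-treatment "events that start from the first administration of any trial medication until 30 days (REP) after the last administration". This agrees with the protocol's period-assignment sentence and is not itself in conflict, but it has no worsening exception either.

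SAP 4 (Changes in the planned analysis) says "All analyses described in the CTP will be carried out" and then names two departures: which ECG time points are analysed, and the cancellation of Part C. It does not mention the AE definition.

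**The concern.** The two definitions cannot both be programmed as written. Take a patient with Grade 1 nausea that starts during screening and becomes Grade 3 after dosing. Under the protocol this is a treatment-emergent AE. Under the SAP, if the database holds it as one record with the screening start date, it is a screening event.

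The events at issue are foreseeable. AEs are collected "From signing the informed consent onward until the end of treatment including residual effect period", so pre-dose onsets will be in the database. Protocol 6.2.1.1 sets screening at 1 to 28 days and lets it be extended to 12 weeks in total.

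The safety analysis of this first-in-human trial is descriptive by design, so these tables are a main safety output. An omission of this kind would leave some worsening under treatment out of them, and a reader relying on SAP 4 would not know.

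**Working it through.** The plan states no figure for this point. The check is a comparison of the two rules, followed by the weight of one patient.

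**1. The rules as sets.** Let A be AEs with onset from first dose to 30 days after last dose. Let B be AEs with onset before first dose that worsen on treatment.

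- Protocol 7.3.4: A ∪ B
- SAP 7.8.1: A

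On the same date basis, the SAP set lies inside the protocol set and the difference is B.

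**2. From events to patients.** SAP 7.8.1 says "All analyses will be based on the number of patients with AEs (not on the number of AEs"). For any any-grade row, the protocol count minus the SAP count is therefore the number of patients whose only qualifying events in that row are in B. That number is zero or more.

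**3. How the worsening is recorded.** If it is entered as a new record with a post-dose onset, it falls in A and both rules count it. The SAP would not merge it with the earlier record, because records "are collapsed into one AE event if all AE attributes are identical", and severity is one of those attributes. If the grade change is kept on the original record, the event stays in B and only the protocol counts it.

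**4. Check by enumeration.** Six record types cover pre-dose onset (worsening or not, one record or split), on-treatment onset and post-treatment onset. A patient with one to three AEs has 6 + 36 + 216 = 258 ordered profiles. A patient goes uncounted under the SAP if every record is one of 4 types, and under the protocol if every record is one of 3. The SAP count is lower in (4 − 3) + (16 − 9) + (64 − 27) = 1 + 7 + 37 = 45 profiles, equal in 213 and higher in 0. These are logical possibilities, not probabilities.

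**5. By-grade rows.** A by-grade row changes only if the omitted event would have set the patient's grade. The patient then appears at a lower grade or not at all, so a lower-grade row can gain a patient. The equal-or-lower statement is therefore limited to any-grade rows. The separate screening displays can hold more events under the SAP rule.

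**6. Weight of one patient.** AE tables use the treated set (SAP 7.8), which contains the MTD Evaluation Set (SAP 6.3). Each treated n is at least the evaluable n in protocol Tables 7.1.2: 2 and 7.1.2: 5, so one patient contributes at most 1/n.

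| Group | Evaluable n | 1/n, points |
|---|---|---|
| Part A 25, 100, 200 mg | 3 each | 33.3 |
| Part A 50 mg | 4 | 25.0 |
| Part A 400 mg | 6 | 16.7 |
| Part A total (2+1+3+4+3+3+6) | 22 | 4.5 |
| Part B 50 mg | 6 | 16.7 |
| Part B 200 mg | 8 | 12.5 |
| Part B 400 mg | 5 | 20.0 |
| Part B total (6+8+5) | 19 | 5.3 |

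The 5 mg and 15 mg cohorts had 2 and 1 evaluable patients. The Part B numbers are as of 13 November 2019 and include no b.i.d. cohort; 31 to 37 patients are planned for that part.

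**The case against.** **The SAP takes in the protocol by reference.** SAP 3 says it builds on protocol Section 7, and SAP 4 promises all protocol analyses, so 7.8.1 could be read as an incomplete restatement. This does not settle the matter. 7.8.1 gives its own specific definition and sends screening-onset events elsewhere without exception, and a general statement of reliance does not override it.

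**The worsening may be a new record anyway.** Protocol 5.2.6.7.3 has worsening of pre-existing conditions recorded as an AE, and the SAP's collapsing rule presupposes records of the same AE that can differ in severity. This stands as a reason why the effect may be nil. But nothing in either document requires a new record with its own onset when an AE that began between consent and first dose worsens later. The sponsor's AE standard cited in SAP 7.8.1 may cover it, but it cannot be seen here.

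**The exposed group is small.** Extended screening is partly meant to let an AE recover before dosing, so many such events will have resolved. Laboratory worsening is also captured by the change-from-baseline summaries and shift tables of SAP 7.8.2. Both points stand and limit the consequence.

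**Stronger readings that a reader might infer.**

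- *That SAP counts can never exceed protocol counts, so any error must understate toxicity.* SAP 7.8.1 starts its period on the date of first administration. Read by date, an AE beginning on Day 1 before the dose counts under the SAP. Read by time, the protocol would exclude it unless it worsened. Partial AE dates are also imputed by a sponsor standard not available here. The direction holds only on a common date basis.
- *That a cohort's AE rate could be understated by a third.* The 1/n figures show what any one patient contributes to any row. They are neither a bound on several patients together nor an expected effect.
- *That DLT counts or the MTD are affected.* DLTs follow their own definition and review in protocol 4.1.8, and no route from the treatment-emergent definition to those counts is shown.

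**Conclusion.** The point holds as an undeclared conflict between two stated rules. SAP 7.8.1 omits the protocol's deterioration clause, and SAP 4 does not say so. Confidence in the textual difference is high.

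The consequence is narrower. In Parts A and B, with both rules applied on the same date basis, any-grade patient counts can be equal to or lower than under the protocol rule. A row is lower only when both conditions hold: the worsening stays on the pre-dose record, and the patient has no other qualifying AE in that row. The frequency is unknown and may be zero. Part C is cancelled and unaffected.

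The conclusion assumes that the unseen sponsor standard and the eCRF do not already force a new record at each worsening. If they do, the counts agree and only the SAP wording needs correcting. It should be fixed because it is cheap and the cohorts are small.

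**What to change.** Restore the deterioration clause in SAP 7.8.1, with a cross-reference in 6.1, so that AEs starting before first dose and worsening on treatment enter the treatment-emergent tables, using worsening as recorded in the eCRF. In the same edit, say whether a Day 1 onset is judged by date or by time.

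Two alternatives would also remove the conflict. The SAP could state that a worsening after first dose is always recorded as a new AE with its own onset date, if that is the practice. Or, if onset only is intended, SAP 4 could declare it as a change from the protocol.

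The cost is a sentence, a programming flag and a check of how grade changes are recorded; the source-document examples in protocol 8.3.1 mention only onset and end dates for AEs. Reported AE rates may rise slightly.

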7.8.2 Laboratory data

The analysis of laboratory data will be descriptive in nature and will be based on BI standards (7). The same on-treatment period as considered for the analysis of adverse events will be applied for laboratory values. Patients having at least one post-baseline laboratory value will be displayed in the descriptive analyses. Patients with missing CTCAE grade at baseline or no baseline value but with post-baseline values will be displayed in a new category “missing CTCAE grade at baseline” for those laboratory parameters where CTCAE grading is applicable. CTCAE grades for applicable laboratory parameters will be calculated according to CTCAE v5.0.

For Primary laboratory tests listed in Table [7.8.2: 1](#), the following outputs will be presented:

- Descriptive statistics, including changes from baseline
- Shift tables in terms of:
 - CTCAE grade, for laboratory tests with CTCAE grade defined;
 - Upper and lower reference limits, for laboratory tests without CTCAE grades;
 - Multiples of upper reference limit for customized shift tables of ALP, ALT, AST, bilirubin and creatinine.
- Frequency of patients with potential clinically significant abnormalities.

For secondary laboratory tests listed in Table [7.8.2: 2](#), analyses will be limited to frequency of patients with potential clinically significant abnormalities.

For other laboratory tests, only listing of observed values will be presented.

Analyse of descriptive statistics should use normalized lab values. Analyses of frequencies of patients with potential clinical significance, analyses of shift, and liver function categories tables should use converted values.

Table 7.8.2: 1 Primary laboratory tests

Label	Lab test name	Direction of interest	Potential Clinical significance rule
A1AGLP	Alpha-1 Glycoprotein	High ⁴	>ULN and >baseline No CTCAE defined
ALP	Alkaline Phosphatase	High	CTCAE Grade 2 or higher ³
ALT	Alanine Aminotransferase	High	CTCAE Grade 2 or higher ³
AST	Aspartate Aminotransferase	High	CTCAE Grade 2 or higher ³
BILI	Total Bilirubin	High	CTCAE Grade 2 or higher ³
BILIND	Indirect Bilirubin	High	CTCAE Grade 2 or higher ³ using grades defined for Total Bilirubin
BILDIR	Direct Bilirubin	High	CTCAE Grade 2 or higher ³ using grades defined for Total Bilirubin
CK	Creatine Kinase	High	A ^{1,2}
CREAT	Creatinine	High	>1.5xULN and >baseline Ambiguous CTCAE not used ³
GLUC	Glucose	Low, High ⁴	Low: A ^{1,2} High: >10 mmol/L and > baseline No CTCAE defined
HAPTOG	Haptoglobin	Low ⁴	<LLN and <baseline No CTCAE defined
HGB	Hemoglobin	Low	A ^{1,2} (listed in CTCAEv5 as “Anemia”)
K	Potassium	Low ⁴ , High	Low: <3 mmol/L and <baseline High: A ^{1,2}
LDH	Lactate Dehydrogenase	High ⁴	≥3xULN and >baseline No CTCAE defined
LYM	Lymphocytes	Low	A ^{1,2}
NEUT	Neutrophils	Low	A ^{1,2}
PLAT	Platelets	Low	A ^{1,2}
RETI	Reticulocytes	Low ⁴	<LLN and <baseline No CTCAE defined
SODIUM	Sodium	Low ⁴ , High	Low: <130 mmol/L and <baseline High: A ^{1,2}
T3FR	Triiodothyronine, Free	Low ⁴ , High ⁴	Low: <LLN and <baseline High: >ULN and >baseline No CTCAE defined
T4FR	Thyroxine, Free	Low ⁴ , High ⁴	Low: <LLN and <baseline High: >ULN and >baseline No CTCAE defined
TSH	Thyrotropin	Low ⁴ , High ⁴	Low: <LLN and <baseline High: >ULN and >baseline No CTCAE defined

Table 7.8.2: 1 Primary laboratory tests (cont')

Label	Lab test name	Direction of interest	Potential Clinical significance rule
UREAN	Blood Urea Nitrogen	High ⁴	>10 mmol/L and >baseline No CTCAE defined
WBC	Leukocytes	Low	A ^{1,2}

¹A= CTCAE grade 2 or greater with an increase of at least one CTCAE grade from baseline

²Separate shift tables for the low and high directions, when both directions are specified. Shift tables compare baseline vs. on-treatment CTCAE grades. CTCAE grading will not consider symptoms.

³CTCAE grades will not be defined for baseline values for ALP, ALT, AST, BILI (total, direct, and indirect) and CREAT. Special categories are defined for shift tables.

⁴Separate shift tables for the low and high directions, when both directions are specified. Shift tables compare baseline vs on-treatment using the three categories (1) below reference range, (2) within reference range, and (3) above reference range.

Table 7.8.2: 2 Secondary laboratory tests

Label	Lab test name	Direction of interest	Potential Clinical significance rule
ALB	Albumin	Low	A ¹
APTT	Activated Prothrombin Time	High	A ^{1,2}
CA	Calcium	Low, High	A ¹
CHOL	Cholesterol	High	A ¹
CL	Chloride	Low, High	Low: <80 mmol/L and <baseline High: >120 mmol/L and >baseline No CTCAE defined
EOS	Eosinophils	High	>1.0 10**9/L and > baseline No CTCAE defined
INR	Prothrombin Normalized ratio	High	>1.5 and >baseline
PHOS	Phosphate	Low, High	High: >1.7 mmol/L and >baseline Low: <0.7 mmol/L and <baseline
PROT	Serum Protein	High	>ULN and >baseline No CTCAE defined
PT	Prothrombin Time	High	>ULN and > baseline No CTCAE defined
TRIGL	Triglycerides	High	A ¹
UREA	Urea	High	>1.5 x ULN and >baseline No CTCAE defined
URATE	Uric Acid	High	Females: >600 umol/L and >baseline Males: >650 umol/L and >baseline CTCAE based upon AE

¹A= CTCAE grade 2 or greater with an increase of at least one CTCAE grade from baseline

²CTCAE grading will not consider symptoms presence of bleeding or use of anticoagulation.

Handling of CTCAE grade -1 and -9 laboratory parameters:

Generally, in case only one direction of worsening (high or low laboratory value) is specified in the CTCAE document, there is no need to examine the other direction. Therefore, for

calculating the change in CTCAE grade, patients with a CTCAE grade of -9 (no CTCAE grade defined) will be automatically treated as CTCAE grade 0 for all analyses. In laboratory listings, the CTCAE grade will be displayed as -9.

There are certain parameters for which CTCAE grades can only be differentiated by taking physiological consequences into account. These laboratory values will be coded as -1. As these definitions aggregate laboratory data and adverse events or concomitant therapies no analyses based on CTCAE grades will be done. Instead standard laboratory analyses as for laboratory parameters without CTCAE grade definitions will be done. Nevertheless, a laboratory listing including -1 values will be added to the CTR.

Corrected calcium:

The grading of hypocalcemia is based on corrected calcium as calcium can be falsely low if hypoalbuminemia is present. The following corrective calculation will be performed:

$$\text{Corrected calcium (mg/dL)} = \text{Total Calcium (mg/dL)} - 0.8[\text{Albumin (g/dL)} - 4]$$

No correction of the reference range has to be done. The reported reference range of total calcium will be used for analyses. Corrected calcium can be only derived at a certain time point in case both laboratory values total calcium and albumin have been reported for the patient in the same laboratory sample.

Hepatic enzyme elevations (potential Hy's law cases):

These are defined as those cases where a combination of all of the following events occurred: any on-treatment value of ALT and/or AST > 3ULN (upper limit of normal) with total bilirubin \geq 2ULN and ALP < 2ULN. The events can occur in any order, but must occur within 14 days of the previous event, i.e. the second event must occur within 14 days of the first event, and the third event must occur within 14 days of the second event, etc. Patients with missing laboratory values for liver enzymes will be excluded from these analyses, but presented separately.

Tabulations of hepatic enzyme elevations and liver laboratory values will be done according to the FDA Drug Induced Liver Injury (DILI) guidance ([10](#)).

Hepatic enzyme elevations will be displayed for the treated set for the whole on-treatment period.

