5.2.3 Safety laboratory parameters

For the sampling time points please see [Part A Flow Chart](#), [Part B Flow Chart](#), and [Part C Lung Flow Chart](#) for each part. All analyses will be performed locally. Patients do not have to be fasted for the blood sampling for the safety laboratory tests.

Instructions regarding sample collection, sample handling/ processing and sample shipping are provided in the Laboratory Manual in the ISF.

Clinically relevant abnormal findings as judged by the Investigator will be reported as adverse events (please refer to Section 5.2.6).

In case the criteria for hepatic injury are fulfilled, a number of additional measures will be performed (please see Section 5.2.6.4.5 and the Potential DILI Checklist provided in the ISF). The amount of blood taken from the patient concerned will be increased due to this additional sampling.

Safety laboratory tests will include the following parameters:

Haematology

The standard haematology panel will consist of: haemoglobin, red blood cell count, haematocrit, mean corpuscular volume, white blood cell count, differential blood count (preferably expressed in absolute values), platelets, haptoglobin and reticulocytes.

Biochemistry

The standard biochemistry panel will consist of glucose, sodium, potassium, chloride, calcium, phosphate, venous bicarbonate HCO₃, creatinine, AST, ALT, alkaline phosphatase, lactate dehydrogenase, total, direct and indirect bilirubin, total protein, albumin, urea nitrogen (or urea in lieu of urea nitrogen), uric acid and creatinine kinase (CK). If CK is elevated, then CK-MB [cardiac], Troponin I/Troponin T, and myoglobin should be reactively tested.

A thyroid panel (TSH, free T4, and free T3) will be done during Parts B and C at the time of each standard biochemistry panel.

If symptoms of pancreatitis are observed, amylase and lipase should be tested at the discretion of the Investigator.

Coagulation

Activated partial thromboplastin time (aPTT) and prothrombin time (PT) (expressed either in seconds or as percentage) will be tested according to the timing in [Part A Flow Chart](#), [Part B Flow Chart](#), and [Part C Lung Flow Chart](#).

Urine

Urine (pH, glucose, erythrocytes, leukocytes, protein, and nitrite) will be analysed by dipstick (semi-quantitative measurements).

Pregnancy test

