Rationale for change		Update BI 891065 tablet strengths in this study because 100 mg tablet will become available. It will not be distributed to countries until all local regulatory requirements for adding a new dose strength are met.
Section to be changed		Figure 4.1.7: 1 Schematic of dose delays and reductions
Description of change		Modified box BI 891065: Restart at original dose or at one dose level lower* Figure footnote: If deemed Investigator to decide based on what is in the best interest of the patient, may restart at original assigned dose.
Rationale for change		To clarify criteria for restarting at original or a lower dose after a dose interruption
Section to be changed		Figure 4.1.7 Dose reduction and dose delays
Description of change		A maximum of 2 dose reductions of BI 891065 are allowed, if lower tested dose levels are available. Dose reductions will be only to doses previously explored in earlier cohorts if the Investigator anticipates a lower dose would be better tolerated.
Rationale for change		To clarify criteria for dose reduction of BI 891065
Section to be changed		Section 5.2.3 Safety laboratory parameters
Description of change		The standard haematology panel will consist of:

		haemoglobin, red blood cell count, haematocrit, mean corpuscular volume, white blood cell count, and differential blood count (preferably expressed in absolute values), and platelets, haptoglobin and reticulocytes.
Rationale for change		To investigate the reason for isolated bilirubin increases observed.
Section to be changed		Section 5.2.4 Electrocardiogram
Description of change		In Part C, single ECGs will typically be taken unless additional triplicate readings are required with pharmacokinetic sample collection as indicated in Table 10.3: 3. When triplicate ECGs are not done, single readings will be done for safety purposes as indicated in Part C Lung Flow Chart.
Rationale for change		To clarify timing of single and triplicate ECG collections in Part C.
Section to be changed		Section 5.2.6.4.3 Cytokine release syndrome

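### The SAP's reticulocyte abnormality rule looks only for low values, so a rise is left out of the abnormality counts and could be missed in the shift table

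*SAP*

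**What the plan says.** The haematology panel in Protocol Section 5.2.3 ends with "differential blood count (preferably expressed in absolute values), platelets, haptoglobin and reticulocytes". Protocol Section 11 records that global amendment 5, dated 26 July 2019, added the last two tests, and it states the purpose: "To investigate the reason for isolated bilirubin increases observed". The amendment entry is cited here for purpose only; the panel and the SAP rows are current text.

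SAP Table 7.8.2: 1 (primary laboratory tests) gives reticulocytes a single direction of interest, "RETI Reticulocytes Low". The full rows for the two added tests are:

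- "RETI Reticulocytes Low ⁴ <LLN and <baseline No CTCAE defined"
- "HAPTOG Haptoglobin Low ⁴ <LLN and <baseline No CTCAE defined"

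For primary tests, SAP Section 7.8.2 plans three kinds of output:

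- "Descriptive statistics, including changes from baseline".
- Shift tables, which for ungraded tests are based on "Upper and lower reference limits, for laboratory tests without CTCAE grades".
- A count of patients who meet the clinical-significance rule in the last column of the table.

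Footnote 4, attached to the reticulocyte row, makes two provisions. Low and high shift tables are separated where a test has both directions. The shift categories are below, within and above the reference range.

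**The concern.** When red cells are destroyed and the marrow responds, haptoglobin falls and reticulocytes rise. That is general physiology and is not stated in either document, but it is the natural reason for pairing the two tests in a search for the cause of raised bilirubin. The SAP gives haptoglobin the direction that fits this search and gives reticulocytes the opposite one. A low reticulocyte count bears on marrow suppression, which is a different question.

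At stake is how one output will be read. A frequency table with no reticulocyte increases could be taken as evidence against a marrow response, although the rule cannot register one. Unexplained bilirubin increases had been observed when the tests were added, and autoimmune haemolytic anaemia is on the list of immune-related events of special interest in Protocol Appendix 10.1.

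**Working it through.** There is no figure to reproduce. The check sets the rows of the table side by side and traces a rise through each planned output.

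**Step 1. Direction of the markers in SAP Table 7.8.2: 1**

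| Test | Direction in SAP | Direction expected in haemolysis (general physiology) |
|---|---|---|
| Haptoglobin | Low | Low |
| LDH | High | High |
| Indirect bilirubin | High | High |
| Haemoglobin | Low | Low |
| Reticulocytes | Low | High |

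Four of the five match. Reticulocytes do not.

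**Step 2. Does the SAP justify a single direction?** Section 7.8.2 says that the other direction need not be examined when CTCAE defines worsening in only one. The reticulocyte row states that no CTCAE grade is defined, so that clause does not apply. TSH, free T3 and free T4 also have no CTCAE grade, and each has both a low rule and a high rule (above ULN and above baseline).

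**Step 3. Trace a rise through the outputs.** Take a hypothetical patient whose reticulocytes are within range before dosing, above ULN at one on-treatment visit, and within range afterwards.

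- *Abnormality frequency table.* The rule requires a value below LLN and below baseline. No value qualifies, so the patient is not counted. In a hypothetical cohort of 8 such patients (8 being the largest Part B cohort in Protocol Table 7.1.2: 5), the table would show 0 of 8.
- *Separate high-direction shift table.* Not produced, because only Low is specified.
- *Single shift table.* It has an above-range category. If the highest on-treatment value is used, the patient moves from within to above range. If the lowest or last value is used, the patient stays within range and the rise disappears.
- *Descriptive statistics.* The value enters the change from baseline, and SAP Section 7 includes the minimum and maximum in the standard summary set, so the rise can show in the maximum.

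**Step 4. Which value does the shift use?** The visible text does not say. Footnote 4 offers a hint: two shift tables with the same three categories would be identical unless they took different on-treatment values, presumably the lowest for the low direction and the highest for the high direction. On that reading a low-only table uses the lowest value and misses a transient rise. This is an inference from the footnote, not a stated rule.

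**Step 5. Who is affected?** Only patients with reticulocyte data collected after amendment 5. Protocol Appendix 10.5 shows that Part A had reached its 400 mg cohort by 17 October 2018, about nine months before the amendment. Most of the relevant data should therefore come from later Part B patients. Part C enrolled nobody (SAP Section 4).

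**The case against.** The strongest reply is that the SAP already shows reticulocyte increases. A reader of the table might infer that a rise is never counted, or that only means and medians would hint at it. The documents do not support either reading: the footnote 4 shift table has an above-range category, and the summary statistics include the maximum, which in cohorts of 5 to 8 evaluable patients (Protocol Table 7.1.2: 5) can show an individual rise. This stands, subject to the open question of which on-treatment value the shift uses.

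A reader might also infer that the trial cannot answer its bilirubin question, or that haemolysis would go unnoticed. Neither follows. Haptoglobin, LDH, bilirubin and haemoglobin are flagged in the useful direction. Clinically relevant laboratory findings are reported as adverse events (Protocol Section 5.2.3), and autoimmune haemolytic anaemia is reportable as an event of special interest under the criteria in Appendix 10.1. None of this depends on the reticulocyte flag.

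Two further points are fair. The amendment names neither haemolysis nor a direction for reticulocytes. And the laboratory analysis follows a sponsor standard (SAP reference 7) that is not available here and may settle which value enters a shift table. Neither explains why this row lacks a high rule when other ungraded tests have one. The SAP history table shows that Section 7.8.2 was revised on 21 December 2020 to clarify the clinical-significance rules, well after the tests were added.

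**Conclusion.** The concern holds in a narrow form. A reticulocyte rise is excluded from the abnormality frequency table by construction and has no separate high-direction shift table. It remains visible in the descriptive statistics and, depending on an unstated choice of value, in the single shift table.

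The effect is modest. One marker in a descriptive safety analysis points away from the purpose for which it was added, which weakens the investigation of the bilirubin increases without defeating it. No primary or secondary endpoint is touched. The conclusion rests on one assumption from outside the documents, that a rise is the direction of interest when haemolysis is being considered. The change is worth making because it is nearly free, and because a zero in the frequency table would otherwise say nothing about increases.

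**What to change.** In SAP Table 7.8.2: 1:

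- Set the reticulocyte direction of interest to Low and High.
- Keep the low rule and add a high rule of above ULN and above baseline, as already written for TSH, free T3 and free T4.
- Produce the high-direction shift table that footnote 4 then calls for.
- State, for all shift tables, which on-treatment value enters each direction.

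The cost is one table row, one extra output and one clarifying sentence; no new data are needed. The above-baseline condition cannot be evaluated for patients with no reticulocyte value before first dose, which is likely for those who started before amendment 5. The SAP should say how they are shown, since its missing-baseline category covers only tests with CTCAE grades.
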